2.0 Background / Literature Review / Rationale for the study

1. Significance

Invasive melanoma, a lethal form of skin cancer, is the seventh most common cancer in women. The vast majority of melanomas are curable if the cancer is caught early, yet over 10,000 people in the United States are estimated to have died of melanoma in 2017.¹ New opportunities to decrease mortality from this deadly cancer, which is visible on the skin surface, are warranted.

Melanoma incidence increased 3% per year for the last two decades in part due to indoor tanning by young women. In 1994, [name] group found that 24% of teen women in Illinois tanned indoors.² Since 1994, indoor tanning has increased from 24% to 40% among women between the ages of 18 and 30 years old.³ Currently, about 30 million people, most of whom are women, indoor tan every year. Indoor tanning for 10 or more sessions prior to age 30 is linked with a 6-fold increase in the risk

Effect of SSE education delivered during the mammography experience.

of developing melanoma. The Food and Drug Administration recently recognized the need for screening and recommending regular skin exams among women who have tanned indoors. Reaching the vast numbers of at-risk women requires access to large numbers of women, preferably in a supportive health care environment. Because women have screening mammograms every 1-2 years starting at age 40, many at-risk women could become aware of their risk of developing melanoma during their mammogram experience.

Inclusion and exclusion criteria

3.1 Inclusion Criteria for Patient

Women 18 years of age and older, who are waiting to have a mammogram

Women agree to complete informed consent and registration forms allowing follow-up reminders and access to their EMR record limited to the visit with a dermatologist or primary care physician regarding a concerning skin lesion and the results of the biopsy of the lesion.

3.2 Exclusion Criteria for Patient

Women who are unable to see to read a newspaper, unable to read English, and who have cognitive impairment causing problems with functioning at a sixth grade reading level or inability to speak.

3.3 Special populations

Special populations will not be invited to participate in this research.

3.0 Procedures Involved

3.1 Study Design

Phase 1: *Delivery of educational SSE program.*

Each of the eight changing rooms of the Lynn Sage Comprehensive Breast of Northwestern Memorial Hospital will be equipped with a poster, brochures (Fig 1 and Fig 2) and cards with information about obtaining an appointment with a dermatologist for concerning skin lesions.

A woman research assistant will obtain consent to participate in the research and review of medical information, collect contact information and if the woman owns an iPhone X, 8+ or 8, and ensure receipt of an informational brochure. Women will be asked if they own an iPhone X, 8+ or 8 to assess the prevalence of these specific phones in the population of interest. These iPhones models are of particular interest to the research team as they offer superior image quality compared to older models. If a woman has this type of phone, she will be asked about her experience using it to take close-up pictures. The woman will be asked her preference for being contacted by email, telephone, or text message. The two arms of the study will be delivered on different weeks. During weeks 1,3,5 and 7 of the study period 400 women will be given brochures and a card with information on scheduling dermatology follow-up prior to check-out (Group 1), (Fig 3). During weeks 2, 4, 6 and 8 of the study period, 400 women will be given brochures to perform SSE at home and proceed to check-out of the mammogram area (Group 2). The women in Group 1 will also receive a reminder about performing a SSE one week after their mammogram visit via phone call,

Effect of SSE education delivered during the mammography experience.

email or text message. One month after the mammogram visit both groups will be called and surveyed to see if they checked their skin and/or made an appointment to see a dermatologist. Three months after the mammogram, both groups will be asked to participate in a complete survey (either via REDCap or telephone), including whether the women followed up in dermatology and if any concerning lesions were biopsied.

Fig 1. SSE Poster

[figure not shown]
[figure not shown]

Fig 2. Cover of SSE

[figure not shown]

Phase 2: Assessment of SEE Implementation

A research assistant will be present at the mammography center to collect consent, telephone numbers, iPhone model information, and email addresses to have women sign onto REDCap to complete a survey. A telephone survey will be administered to each woman enrolled in the study in both groups (N=800) one month after the mammogram asking if she performed a SSE at home and whether a follow-up with dermatology was made. An anonymous REDCap survey may be used in place of the telephone call, depending on participant's preferred method of contact preference. Then, three months after the screening mammogram, an anonymous <2 minute REDCap survey will be sent via email to each woman enrolled in both groups to ascertain the number of women who identified that they were at increased risk for melanoma (history of sunburn, history of indoor tanning >10+sessions, family or personal history of skin cancer), performed a SSE at home, found a concerning lesion, made a follow-up appointment with a dermatologist, and had any concerning lesions biopsied. If participants do not complete the REDCap survey in 2 weeks, they will be called and surveyed via telephone. We anticipate a 20% attrition rate (Fig 3). Participants will be offered a \$10 Amazon gift card in appreciation of completing the one month survey and an additional \$10 for completing of a second REDCap survey three months after the mammogram visit.

Effect of SSE education delivered during the mammography experience.

Fig 3. CONSORT diagram for two arms of study

Effect of SSE education delivered during the mammography experience.

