1.0 Purpose of the Study

The proposed study is the second phase of a project assessing the feasibility and effectiveness of enhancing the early detection of melanomas among women, who are engaging in health promotion by having mammograms. The initial phase of the project framed risk messages, developed posters and brochures with the input provided by women undergoing screening mammograms, and assessed the feasibility of delivering the program during the mammogram visit at the Lynn Sage Comprehensive Breast Center of Northwestern Medicine/ Prentice Women's Hospital. Now, we seek to evaluate performance of skin self-examination (SSE) by women, who receive information during their mammogram appointment, and follow-up with dermatology for a melanoma screening examination.

In the second phase, a more intensive intervention in which women will not only receive information about SSE, but will also receive a reminder to perform SSE one week after the screening mammogram and information on how to schedule an appointment with dermatology will be provided. The number of women who perform SSE at home and find a concerning mole (lesion), number who see a dermatologist, and number who have a concerning lesion biopsied will be compared in two arms of the study 1) women who receive the intensive intervention 2) women who receive the informational brochure about SSE alone.

Our hypothesis is that women who receive more the intensive educational intervention will be more likely to perform SSE at home and schedule a follow-up dermatologist appointment as compared to those who receive the information brochure alone. This project builds upon [name]'s successful SSE training program for melanoma patients that resulted in patients' accurate evaluations of suspicious lesions relative to dermatologists' skin examinations.⁴

The study aims are as follows:

1. Assess whether SSE education introduced during routine screening mammography encourages women to implement SSE at home, find concerning lesions, and seek follow-up with a dermatologist.
2. Assess the effectiveness of additional reminders to perform SSE and providing information on how to schedule follow-up with a dermatologist on participant performance of SSE with identification of a concerning lesion or scheduling a screening examination with a dermatologist without performing SSE.

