3.2 Informed Consent, Participant Surveys, and Educational Intervention

As patients wait to have the mammogram, they will be screened for eligibility. Following completion of the mammogram, patients will return to the changing room and put on their clothing. After exiting the changing room in the Lynn Sage Comprehensive Breast Center of Northwestern Medicine/Prentice Women's Hospital and as they are preparing to leave, a research assistant (RA) will interview potential participants to acquire a randomly selected convenience sample of eligible participants (n=800). Participants will be invited to complete a survey that will assess knowledge of melanoma and the risk of developing a melanoma. They will be provided with a consent form and the research study will be discussed, questions will be invited and then they will be asked to sign a consent form and to fill out a registration form containing contact information. (see attached)

The complete survey includes general demographic items such as age, education, household income, race and ethnicity. The survey questions are as follows:

1. During your visit for mammography, did you notice any information about checking your skin for melanoma?

Yes No

2. Did you think this applied to you?

Yes No

3. If no, why not? (open ended)

4. If yes, why? (open ended)

5. Did you check your skin? (If no, please proceed to question #7)

Yes No

6. If yes, did you notice any concerning moles?

Yes No

7. If no, will you consider checking your skin in the future?

Yes No

8. If you found any concerning moles, did you make an appointment to see a dermatologist?

Yes No

The RA will record the responses.

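### Dermatology-appointment cards sit in all eight changing rooms with no limit by week, so brochure-only women can obtain part of the intensive intervention and the dermatology comparison may be diluted

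*Combined protocol and SAP*

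**What the plan says.** All references are to the combined protocol and SAP.

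- **Room stock.** Section 3.1 (Study Design, Phase 1) equips each of the eight changing rooms with a poster, brochures and "cards with information about obtaining an appointment with a dermatologist for concerning skin lesions". No week or arm is attached to this.
- **Group 1, weeks 1, 3, 5 and 7.** The same section says that "400 women will be given brochures and a card with information on scheduling dermatology follow-up prior to check-out (Group 1"). These women also get a reminder one week after the visit.
- **Group 2, weeks 2, 4, 6 and 8.** Here "400 women will be given brochures to perform SSE at home and proceed to check-out of the mammogram area (Group 2").
- **Separation of arms.** "The two arms of the study will be delivered on different weeks". Nothing is said about the room stock changing with the week.
- **Purpose (section 1.0).** The comparator is "women who receive the informational brochure about SSE alone". Aim 2 concerns "additional reminders to perform SSE and providing information on how to schedule follow-up with a dermatologist".
- **Visit flow (section 3.2, Informed Consent, Participant Surveys, and Educational Intervention).** "Following completion of the mammogram, patients will return to the changing room and put on their clothing". The research assistant interviews them after they come out.
- **Outcomes.** Section 3.4 (Measures) compares the proportions who performed skin self-examination (SSE) and who saw a dermatologist. Section 14.0 (Data Analysis) names SSE performance, biopsy and diagnoses as primary, and describes the intensive arm as brochure plus reminder, without the card.

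**The concern.** Scheduling information is one of the two things that distinguish the arms in Aim 2. If it is freely available in the control arm's changing rooms, that arm is no longer brochure alone, and any effect of the card is partly present on both sides.

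The outcome most exposed is seeing a dermatologist, which is what the card is meant to promote. Biopsy and diagnoses depend on a dermatology visit, so they are exposed indirectly. SSE performance is less so, because the card concerns appointments and not the examination. Any bias would run toward no difference.

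A null result would then be hard to read: it could mean that the intensive package does not work, or that controls had part of it. None of the survey items printed in sections 3.2 and 3.3 asks about a card, so the data could not tell the two apart.

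**Working it through.** **Step 1: can a Group 2 woman meet a room card?** The room-stock sentence covers all eight rooms and carries no condition. Section 3.2 puts each woman back in a changing room before the interview. Followed literally, every woman in weeks 2, 4, 6 and 8 passes through a room that holds cards. Group 1 women do too, but they are handed a card anyway, so the change in exposure falls on Group 2.

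**Step 2: what stays different between the arms?** Being handed a card, and the one-week reminder, which under section 3.3 also prompts scheduling if a concerning mole is found. The contrast is weakened, not removed.

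**Step 3: what could this cost?** The plan states no alpha, power, expected rates or card uptake, so it has no figure to reproduce. The following is an illustration only.

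- From the plan: 400 per arm and 20% attrition, so n = 400 × 0.8 = 320 per arm.
- Assumed: two-sided 5%, the rates p0 (Group 2) and p1 (Group 1) without leakage, the share of the effect carried by the card, and the share of Group 2 who take and use a room card. Clustering by week is ignored.
- Leakage: L = card share × Group 2 uptake.
- Diluted control rate: q = p0 + L × (p1 − p0). Difference: d = p1 − q.
- Power = Φ{ [d√n − 1.96 √(2 p̄(1 − p̄))] / √[q(1 − q) + p1(1 − p1)] }, with p̄ = (q + p1)/2.

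For 10% vs 18%:

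- L = 0: q = 0.10, d = 0.08. (1.431 − 0.962)/0.487 = 0.963, power 83.2%.
- L = 0.125: q = 0.10 + 0.125 × 0.08 = 0.11, d = 0.07. (1.252 − 0.976)/0.495 = 0.557, power 71.1%.
- L = 0.25: q = 0.12, d = 0.06. (1.073 − 0.990)/0.503 = 0.166, power 56.6%.

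The same formula at other assumed rates:

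| Assumed rates | L = 0 | L = 0.125 | L = 0.25 |
|---|---|---|---|
| 5% vs 10% | 67.1% | 54.1% | 41.1% |
| 10% vs 18% | 83.2% | 71.1% | 56.6% |
| 20% vs 30% | 83.3% | 71.8% | 57.8% |
| 10% vs 20% | 94.5% | 86.4% | 73.1% |
| 20% vs 35% | 99.0% | 95.9% | 88.0% |

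**Step 4: what uptake do these leakages need?** If the card carries half the effect, L = 0.125 needs 25% uptake and L = 0.25 needs 50%. If it carries a quarter, they need 50% and 100%. At 10% uptake L is only 0.025 to 0.05, and power for 10% vs 18% is 81% to 79% against 83%. Low uptake costs little.

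**The case against.** The strongest reply is that this is an inference from silence. The opening sentence of section 3.1 may simply list programme materials, and delivering the arms in different weeks is compatible with changing the room stock each week. Group 1's card is tied to Fig 3, the diagram of the two arms, of which only the caption ("Fig 3. CONSORT diagram for two arms of study") is visible. The inside of the brochure is not visible either; if it already gives dermatology contact details, a room card adds little. The plan also does not say that the room card and the handed card are the same item, or that Group 2 may not have one. These points stand as limits. They do not settle the matter, because no text says that the stock rotates and both cards carry information on getting an appointment.

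The Data Analysis section, which names only the reminder as the difference, could be read as meaning that cards are available to everyone. That would remove the conflict with the room-stock sentence, but not with section 1.0 or Aim 2.

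It is also fair that the power figures depend on the rates chosen. Pairs that start near 80% make the loss look uniform. With a larger true effect the trial absorbs it (20% vs 35% keeps 88.0% at 25% leakage), and 5% vs 10% is underpowered with no leakage at all.

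Finally, Group 2 is not shut off from dermatology in any case: section 10.0 has control subjects who are worried about a lesion told to make an appointment.

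**Conclusion.** The point holds as an avoidable opportunity for dilution. Current sections conflict on whether the brochure-only arm has access to scheduling information, and followed as written the plan gives Group 2 access to a component that Aim 2 tests. The comparison affected is seeing a dermatologist, which section 3.4 compares but section 14.0 does not list as primary. Biopsy and diagnoses, which are primary, are affected only through it.

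The size cannot be stated. Under the assumptions above, the loss runs from two to four percentage points of power at 10% uptake (10% vs 18%) to about 27 points at 25% leakage (83.2% − 56.6%), and it depends on the true effect.

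A reader might infer that contamination will occur, that the two arms are effectively the same, or that the trial loses most of its power. The documents support none of these. They give no uptake, the handed card and the reminder stay unique to Group 1, and large losses need both high uptake and a card that carries much of the effect.

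**What to change.** **Preferred.** In section 3.1, stock the changing rooms with the poster and brochures only, and state that the research assistant holds the appointment cards and gives them to Group 1 women. At the least, state that cards are kept out of the rooms in weeks 2, 4, 6 and 8. Then reconcile section 14.0 with sections 1.0 and 3.1 by naming the card in the intensive arm: brochure, appointment card and one-week reminder versus brochure only.

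**Cost.** One sentence and one phrase, with a research assistant who is already on site. The downside is that women using the rooms, including those not in the study, lose passive access to the card. Removing cards only in Group 2 weeks halves that loss but needs a weekly change in eight rooms.

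**If room cards must stay.** Restate the contrast as handed card plus reminder versus brochure with passive card access. Add one yes/no question on whether the woman took an appointment card from the changing room, asked at the visit before any card is handed out, and report it by arm. With 400 Group 2 women the 95% half-width, 1.96√(p(1 − p)/400), is 2.9 points at 10% pickup, 4.2 at 25% and 4.9 at 50%.

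First settle when the section 3.2 survey is given. Section 12.0 calls the one-month contact the second survey, which suggests that the first is at the visit. But section 3.1 uses the term complete survey for three months, and the section 3.2 items on having checked the skin and made an appointment fit poorly with women who are just leaving. This alternative gives a weaker contrast, and the question may itself prompt some Group 2 women to ask for a card.

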3.4 Measures

The number of women with risk factors for melanoma, who performed SSE after the screening mammogram, who found a concerning mole, who saw dermatology, who had a concerning lesion biopsied in each group will be analyzed by descriptive statistics. The difference in proportions of women who 1) performed SSE 2) saw a dermatologist in the educational intervention group from the intensive intervention group will be compared using a χ^2 test. If the woman responded “yes” to follow-up in dermatology, a chart review of the electronic medical record will be performed to assess whether any lesions were biopsied and pathology of the concerning lesions. The accuracy of the woman’s selection of a concerning lesion will be assessed by examining the correspondence rate between the woman’s assessment during SSE and the dermatologist. The overall correspondence rate will be calculated with a random intercept-only mixed logistic regression model. The statistical analysis will be performed by [name], MPH.

Online data

REDCap survey (see page 8 above)

Approvals required

Effect of SSE education delivered during the mammography experience.

[name] obtained permission for this research to be conducted in the Lynn Sage Comprehensive Breast Center of Northwestern Medicine/Prentice Women's Hospital

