5.0 Recruitment

7.1 Recruitment of Patients

A woman research assistant will perform in-person interviews with participants to ascertain if women is eligible for the study and interested to participant. Women who sign written consent and fill out a registration form will be entered into the study. (n=800) (see attached forms)

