14.0 Data Analysis

14.1. This convenience sample of women undergoing screening mammography will all receive education either as a brochure and a 1-week reminder or as only the brochure. Demographic characteristics of the two groups will be examined using means and standard deviations (age) and counts and percentages for all categorical variables. Primary outcomes of SSE performance, biopsy, and diagnoses will be compared using Chi-square tests of association or Fisher's exact tests where sample sizes were restrictive. Due to the skewed nature of the anxiety scale, a Wilcoxon rank sum test will be used to compare anxiety, the secondary outcome, in the two groups. Descriptive statistics will be performed for the tertiary outcome of dissemination.

15.0 Confidentiality and Data Management:

1. There are no biological specimens. All of the following data is collected in person consent and responses to structured interviews and focus groups.
2. Our systems are guarded against outside entry by Northwestern's own firewall supporting 128-bit encryption. This level of encryption provides the highest level of protection against hackers, computer break-ins, etc. All data is deidentified. Experienced research assistants will be employed and will receive training that includes emphasis upon the importance of confidentiality of information, and all personnel on the project will complete the required NIH training in the protection of human research participants.
3. Data will be retained in separate locked file cabinets and on computers with restricted and password protected access, without links to the master code list. All data based on the research will be reported in aggregate form. No individual respondents will be identified. Electronic data will be maintained in a study specific database on the server of the Department of Dermatology at the Feinberg School of Medicine. Paper-based files will be kept in a locked cabinet in a locked room within the Northwestern University Department of Dermatology research offices. Identifiable data will be kept separate from the case report forms and source documents. Data gathered as a result of this study are available to inspection on request by Food and Drug Administration or other government regulatory agency auditors, and the Northwestern University Institutional Review Board (IRB).

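### Arms alternate by calendar week in a fixed, predictable order, so a recruiter of a convenience sample can be expected to know the arm before each approach, and no between-arm analysis adjusts for differences in who is enrolled

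*Combined protocol and SAP*

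**What the plan says.** **Allocation.** Section 3.1 (Study Design) says "The two arms of the study will be delivered on different weeks". It continues: "During weeks 1,3,5 and 7 of the study period 400 women will be given brochures and a card" on scheduling dermatology follow-up (Group 1). Another 400 women in weeks 2, 4, 6 and 8 receive brochures only (Group 2). Group 1 also gets a reminder at one week. No section describes random assignment or concealment.

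**Recruitment.** Under section 3.2 (Informed Consent, Participant Surveys, and Educational Intervention), a research assistant meets women after the changing room and "will interview potential participants to acquire a randomly selected convenience sample of eligible participants (n=800"). Section 7.1 adds: "A woman research assistant will perform in-person interviews with participants to ascertain if women is eligible for the study". Section 14.0 calls the sample simply one of convenience.

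**Analysis.** Section 14.0: "Primary outcomes of SSE performance, biopsy, and diagnoses will be compared using Chi-square tests of association", or Fisher's exact tests. Anxiety is compared by a Wilcoxon rank sum test. Section 3.4 (Measures) plans a chi-square test for "The difference in proportions of women who 1) performed SSE 2) saw a dermatologist in the educational intervention group" against the intensive group. The only model, in section 3.4, is intercept-only and estimates a correspondence rate; it has no arm, covariate or week term.

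**Balance.** Section 14.0: "Demographic characteristics of the two groups will be examined using means and standard deviations (age"), with counts and percentages for categorical variables. Section 3.4 also describes melanoma risk factors in each group.

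**Cards.** Section 3.1 equips all eight changing rooms with "cards with information about obtaining an appointment with a dermatologist for concerning skin lesions".

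**The concern.** Aim 2 (section 1.0) concerns the effectiveness of the added reminder and scheduling information, so the arm comparison answers a core question. When the calendar fixes the arm and the sample is one of convenience, the recruiter has both the knowledge and the latitude to approach or encourage women differently in intensive weeks, without meaning to. Women already inclined to skin self-examination (SSE) could then be more common in one arm. An unadjusted test cannot separate that from an intervention effect, and a larger sample does not shrink the bias. Alternating the weeks gives no protection, because the recruiter's knowledge alternates with the arm.

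**Working it through.** **1. The plan's own figures.** 400 + 400 = 800, as stated. With the 20% attrition of section 3.1, 800 × 0.8 = 640, or 320 per arm. Four weeks per arm gives 400 / 4 = 100 women per week, or 80 after attrition. N = 800 cannot be re-derived: no alpha, power, SSE rate or effect size is given. Figure 3 (the CONSORT diagram) could not be read and is not relied on.

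**2. Does the recruiter know the arm?** The week defines the arm, the order is fixed, and Group 1 receives the card before check-out. The research assistant role takes consent and ensures receipt of the brochure (section 3.1), and gives the Group 1 reminder (section 3.3). Knowledge of the arm is nowhere stated but follows closely from this.

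**3. What differential recruitment would do (every input assumed).** Spurious difference = imbalance in the share of inclined women × gap in their SSE rate. Take 320 per arm, a mean rate of 30%, two-sided alpha 0.05 and no true effect. The standard error is √(2 × 0.30 × 0.70 / 320) = 0.0362. Rejection ≈ Φ(d/0.0362 − 1.96) + Φ(−d/0.0362 − 1.96).

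| Imbalance × gap | Spurious difference d | d / 0.0362 | Rejection |
|---|---|---|---|
| none | 0 | 0 | 5.0% |
| 0.05 × 0.20 | 0.01 | 0.28 | 5.9% |
| 0.10 × 0.30 | 0.03 | 0.83 | 13.1% |
| 0.15 × 0.40 | 0.06 | 1.66 | 38.1% |

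The last row needs both assumed extremes together.

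**4. Would a week-level analysis cure this?** No. With no week effects, a t-test on the eight weekly proportions (6 df) rejects about 11% of the time at the 3-point bias and 29% at 6 points. The fall from 13% and 38% is lost power, not removed bias.

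**5. Week effects, a separate and conditional matter.** With independent weeks, the variance of the arm difference is inflated by 1 + 79 × ICC. For assumed ICCs of 0.001 to 0.02 this is 1.079 to 2.58, and the size of the planned test, 2 × [1 − Φ(1.96/√inflation)], is 5.9% to 22%. At lag-1 correlation 0.95 between weeks it is 5.0% to 5.6%, because alternation largely cancels slow trends. At ICC 0 it is 5%.

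The power cost of a week-level test also varies. Take assumed rates of 30% v 40.6%, where the individual test has 80% power. Week-level power is 65.5% at ICC 0. At ICC 0.01 it is 43% with independent weeks, but about 52% at lag-1 correlation 0.8 and 61% at 0.95.

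**6. Cost of same-day exposure under individual randomisation.** If 5% of Group 2 received the full Group 1 effect, the Group 2 rate becomes 0.30 + 0.05 × 0.106 = 0.3053. Power against 0.406 with 320 per arm falls from 80% to 76%.

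**The case against.** Bias is possible, not shown. No section describes selecting women differently by arm; eligibility, consent, brochure and gift cards are the same in both. Section 3.2 calls the sample randomly selected. Demographics and melanoma risk factors will be described by group. Separating arms by week limits cross-arm exposure and cancels slow trends, and if there is neither selection nor a week effect the planned test is valid at full power.

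Most of this stands as a limit on strength. The phrase about random selection does not rebut the point: it concerns sampling rather than assignment, comes with no mechanism, and is coupled with convenience. Descriptive tables can show imbalance but do not correct it.

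Some stronger readings are tempting. A reader might infer:

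- that the plan presents the allocation as randomised; the documents never call it that.
- that women know their arm before consenting; no section says so.
- that the recruiter does select by arm, or that 38% estimates the error rate; the documents support only the opportunity.
- that the chi-square tests are invalid for want of a week term; that depends on an ICC and autocorrelation the documents do not give.

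**Conclusion.** The point holds as a design weakness that the analysis does not repair: predictable allocation, discretionary recruitment and wholly unadjusted between-arm tests. Any differential recruitment would be reported as intervention effect. Its size cannot be determined from the documents; the 6% to 38% range rests entirely on assumed imbalances, outcome gaps and a 30% mean rate, and the excess over 5% vanishes if recruitment does not differ by arm. That the recruiter knows the arm is a strong inference, not a stated fact. It should be fixed, with medium confidence. Clustering by week is secondary.

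**What to change.** **Preferred.** After consent, randomise each woman 1:1 from a concealed permuted-block list in REDCap and keep the individual-level test. This is feasible: section 3.2 places consent after the changing room, and the handed card and reminder are delivered individually. Give the card only to Group 1 rather than stocking it in the shared changing rooms, where Group 2 can take it. The cost is protocol wording and a randomisation list, with no extra women or visits. The downside is some same-day exposure between arms, illustrated in step 6.

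**Needed for this.** Outcomes must be linkable to arm. Sections 3.1 and 3.3 call the follow-up surveys anonymous, and section 15.0 item 3 stores data unlinked from the master code list. Yet section 15.0 item 5 records data by study number, and the EMR review in section 3.3 acts on survey answers. These passages must be reconciled.

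**If alternating weeks are kept.** Report the comparison as non-randomised. Add an analysis adjusted for characteristics the intervention cannot change (age, education, income, race and ethnicity, all listed in section 3.2), stating that this does not remove unmeasured selection such as motivation or SSE habit. Do not adjust for prior SSE as recalled in item 4 of the three-month survey: it is reported after the intervention and Group 1's reminder, though it may be described by group with that caveat. A week-level or small-sample-corrected clustered analysis is only a sensitivity check for week effects. It does not address recruiter selection, and its need and power cost depend on the unknown ICC and autocorrelation.
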